### **Data acquisition and transmission:**

**Stronghold computing environment:** The very nature of sensitive data requires a highly-protected data silo for it to be housed in. To achieve this objective, the Brown University School of Public Health (BUSPH) will purchase a central storage service hosted by Brown University's Computing & Information Services (CIS) Stronghold secure research computing environment. Stronghold is a HIPAA-compliant, secure computing environment developed for housing, sharing, and analyzing sensitive data. The Data Manager will oversee the database architecture, dataset storage, and all input/output (i.e., data transfer) regulations. Stronghold is a highly secure computer and storage Windows environment for research needs involving sensitive data needing special handling, data usage agreements, etc.

The PI is responsible for maintaining an up-to-date list of accounts that should be able to log into Stronghold, communicating this to the Stronghold Team through the Administrative Contact, and alerting the contact when a user should no longer be allowed access. Users that leave the university will have access terminated along with their Brown account, per CIS Policies: Computing Privileges: Access to Electronic Services.

### **All users must:**

- Complete appropriate training for working with sensitive data (e.g., CITI training);
- Be in compliance with all relevant Institutional Review Board protocols;
- Be in compliance with any data use agreements or other agreements governing the use of the data stored on Stronghold.

**Data Transfers** – There are select methods to import data, including but not limited to:

- Select State offices use a VPN tunnel
- Encrypted USB drives
- Secure transfer through firewall exception
- Import and export servers

### **Termination of Service**

Requests for termination of services should be made to the Administrative Contact. Services will be terminated by the next business day following the request. All data stored on Stronghold that is associated with the terminated account will be deleted upon termination of services.

### **Denial of Access**

If a user fails to comply with the policies and procedures for accessing and using Stronghold, or in the case of a suspected or real security breach, CIS staff can temporarily deny access to Stronghold for the user and suspend all retrieval of information until approval is received from a designated authority.

### **Data Entry Methods**

The project's Database Administrator will manage the database architecture, dataset storage, and all input/output (i.e., data transfer) regulations. The Research Assistant will conduct and automate secure data transfers with data-sharing partners across the state monthly, quarterly, or annually (depending on the Data Use Agreement with each data-sharing partner).

### **Data Analysis Plan**

The quality of the data will be monitored semi-annually. The study's Data Analyst will analyze the data using SAS, R, ArcGIS, and Tableau software within the Stronghold computing environment.

## **C. Quality Assurance Plan**

### **Database Management**

The Data Manager and Stronghold staff will manage the database architecture, dataset storage, and all input/output (i.e., data transfer) regulations. The database will be maintained under several firewalls, with restricted access to the Internet, except for data imports and software installations. Control systems will be implemented to prevent data migration without authorization, complete with real-time notifications of breaches. Additionally, records pulled by approved BUSPH researchers will go through an automated de-identification process to ensure sensitive data cannot be unauthorizedly extracted from the secure server. The data will routinely undergo backup procedures to ensure that the data is recoverable in the event of system failure.

### **Data Quality and Data Protocol Monitoring**

Periodic scanning of Stronghold servers will be done to identify potential security vulnerabilities. The Stronghold Team will attempt to make this service available as requested 24 x 7 x 365 at all times outside the planned maintenance window.

The Stronghold Team monitors and records all activity on the Stronghold system, including networking and access events, which may depend on the classification of the data and any applicable regulations. Project staff receive notification of any activity on the Stronghold system.

### **Protocol Deviations and Noncompliance Reporting**

Protocol deviations and noncompliance reporting will be the responsibility of the Project Investigator and Project Director. Such issues will be monitored consistently, and if any deviations are found, they will be reported promptly to the Brown IRB.

## **D. Regulatory Issues**

### **Reporting of Unanticipated Problems**

The overall data and safety monitoring will be the responsibility of the co-Principal Investigator (PI), [name] [name]. The co-PI is also responsible for executing the Data and Safety Monitoring (DSM) plan and complying with the reporting requirements. The PI will summarize the DSM report to the National Institute on Drug Abuse (NIDA) annually as part of the progress report.

The PI will ensure that all study procedures are in place before initiating the protocol and that all study procedures and reporting of unanticipated problems are performed according to the protocol. Unanticipated events will be monitored by the investigative teams (at BUSPH and at the Rhode Island Department of Health). In addition, a Data Safety Monitoring Board (DSMB) will provide independent study monitoring, as described below.

The PI will monitor for unanticipated events that change the study risk level. If an unanticipated event occurs that changes the study risk level, the Study PI will immediately report this event to the IRB (Brown University), DSMB, and NIDA and will oversee the process of modifying the study as appropriate to address the change in risk. The PI will also provide annual reports summarizing unanticipated event data to the IRB.

### **Report of Changes or Amendments to the Protocol**

All changes or amendments to the protocol will be submitted in writing and will receive prior approval from the Brown University IRB.

## **E. Trial Stopping Rules**

The entire trial will stop if any investigator or a member of the DSMB judges it necessary for medical, safety, regulatory, or other reasons consistent with applicable laws, regulations, or good clinical practice. Once a concern of this proportion is raised, the decision to stop the trial will be made through immediate consultation with the IRB, the DSMB, and NIDA.

The trial may be stopped for the following reasons:

1. The occurrence of unanticipated events involving a loss of confidentiality or privacy (e.g., unintended or unauthorized access to the web tool housing model predictions or row-level data used as inputs for the predictive model).
2. The occurrence of unanticipated events involving a disruption to harm reduction service provision as a result of the study (e.g., diversion of resources away from cities/towns randomized to the control arm that would not have otherwise occurred if the study had not been taking place).
3. It becomes clear that successful completion of the study is not feasible due to logistical or administrative reasons (e.g., changes in leadership at the Rhode Island Department of Health, significant changes to the financial resources available to fund harm reduction service provision).
4. If factors external to the study fundamentally change the study's equipoise.
5. If the occurrence of an unanticipated event involves inappropriate access by criminal justice to the PROVIDENT model predictions or any information related to the trial that would not otherwise be granted.

### **Disclosure of any Conflict of Interest**

All data-sharing partners and investigators will agree to specific terms of use for the data according to a signed Data Use Agreement, which includes a request to disclose any potential conflicts of interest.

### **Data Safety**

This project will use Brown University's Stronghold secure computing environment. As described above, this computing environment is HIPAA compliant and has been developed for housing, sharing, and analyzing

sensitive data. Stronghold is customized to the security needs of each project's Data Use Agreements.

## **F. Trial Safety**

### **Classification of Unanticipated Problems:**

While the PROVIDENT trial does not involve direct interaction with individuals receiving harm reduction services, it does change the environment in which these services are provided. As such, changes in risk pertain to the overall safety of these environmental changes to ensure the safety of the individuals receiving these harm reduction services. Unanticipated problems associated with the PROVIDENT trial may be classified as one of the following categories:

#### **1. Loss of Confidentiality**

The intervention will use a web tool and interactive dashboard to visualize the neighborhood-level risk predictions from the PROVIDENT model. The PROVIDENT Web Tool has undergone a security review with Brown Computing and Information Services (CIS) and the Center for Computation and Visualization (CCV). Use of the Web Tool has been approved, and our team has worked carefully to ensure the protection of the model predictions.

We recognize that a loss of confidentiality through unauthorized access to the PROVIDENT Web Tool and model predictions may also result in psychological harm to individuals or in social harm. As such, the Center for Computation and Visualization personnel will be responsible for the system administration. Research staff will have logins to manage data and download data. Individuals accessing the web application will have access to only the required information and share only what is required. Additionally, only select analytic team members will have access to identifiable datasets. All data transfer procedures, analytic plans, and datasets will be approved by the Brown IRB, any additional institutional IRBs, and the DSMB.

**PROVIDENT Web Tool Infrastructure:** The web application is hosted in Firebase, and application data is stored in Firestore. The application is intended to be used exclusively by organizations' personnel (e.g., non-profits helping with opioid overdose prevention). Once an individual has been approved, they may create a username and password. Authentication is managed using Firebase native authentication.

Logged-in individuals interact with a series of surveys approved by Brown IRB that collect information about services and programs for opioid overdose prevention available in corresponding neighborhoods. Approved organizations will also have access to the PROVIDENT model predictions through the use of the web application. Approved Brown researchers will use the data collected to examine what and how many directed overdose prevention activities are driven in part by the PROVIDENT model to measure fidelity and penetration. Finally, using the surveys, we will regularly query organizations that are approved to use the Web Tool about unauthorized use in community settings (e.g., inadvertent sharing of PROVIDENT screenshots during a community meeting).

Data will be downloaded from Firebase to Brown University data servers through provided, secure APIs (including web). Firebase and Firestore encrypt data during transfer and at rest. Firebase is certified under major security and privacy standards. Privacy and security information in Firebase can be found [here](#). Data protection is managed through security rules, which in this particular case are set to only allow write access to users that have passed the simple authentication mechanism.

Center for Computation and Visualization personnel will be responsible for system administration. People, Place, and Health Collective researchers will have logins to manage and download data.

#### **2. Loss of Privacy**

This project uses secondary data exclusively; therefore, the confidentiality of study data is paramount. Our research requires the use of existing surveillance records related to overdose, medical events, and prescribing

events. Access to such records for legitimate research purposes has been approved by our data-sharing partners (including the Rhode Island Department of Health and the Rhode Island Department of Corrections), and our team has worked carefully to ensure the protection of these data.

We recognize that a loss of privacy may also result in psychological harm to individuals or social harm. As such, the Project Investigator will use Brown's state-of-the-art Stronghold computing environment to transfer, analyze, and protect all research data. Data-sharing partners will share only the required datasets and variables. Additionally, only select analytic team members will have access to identifiable datasets. All data transfer procedures, analytic plans, and datasets will be approved by the Brown IRB, any additional institutional IRBs, and the DSMB.

**Research Database Infrastructure:** This project will benefit from and expand upon data security resources provided by the Brown University "Stronghold" computing system. Stronghold is a secure computing and storage environment that enables Brown researchers to analyze sensitive data while complying with regulatory or contractual requirements. Stronghold is currently self-certified to meet the security requirements and controls for HIPAA (Health Insurance Portability and Accountability Act) and is undergoing the certification process for FISMA (Federal Information Security Management Act) and CJIS (Criminal Justice Information Security). We will use the Stronghold secure computing environment to store, maintain, and transfer data between Brown University and data stakeholders, including RIDOH and other state agencies (e.g., Office of the State Medical Examiners, the Rhode Island Department of Corrections).

Stronghold is a secure virtual computing environment designed for remotely analyzing sensitive data. It uses encrypted SSH (Secure Shell) with two-factor authentication for remote access. Access to each virtual network is limited to a single PI and any additional students or staff the PI authorizes in writing to Brown University Computing & Information Services (CIS). The PI enters into a written agreement with CIS that authorized users must comply with all necessary training requirements. CIS staff with access to Stronghold have completed CITI course modules for working with human subjects data, as Brown's Office of Research Protection requires.

Stronghold is accessible only from within the Brown campus network and by Virtual Private Network connections (using two-factor authentication) outside the campus network. All network connections to Stronghold pass through at least two firewalls: a dedicated firewall on the Brown campus network and a host-based firewall in the Stronghold environment.

The Stronghold system is physically located in a locked rack in a CCV-monitored data center on the Brown campus. Only certain authorized CIS staff have access to this locked rack. Entry to the data center is limited to authorized Brown IT personnel and their guests, and all entries are logged.

This service is customized to the needs of individual users and their data use agreements. Each investigator is given a dedicated environment for their project to support their co-investigators, graduate students, research assistants, interviewers, and other collaborators. Access to the Internet is restricted except for required locations for data imports or necessary software downloads. Import and export controls are in place to limit who can perform data migration, where sensitive data can come from, and where desensitized or anonymized data can be moved. Sensitive data is subject to file system auditing, and real-time alerting is available at the request of the PI.

**Stronghold Data Security Policies for Investigators:** The PI may impose additional requirements regarding credentials, connection methods, or clients based on the nature of the data. All systems (workstations, laptops, etc.) used to connect to Stronghold must have the following security precautions in place:

- a. A password-protected lock-out screen that appears after inactivity of 5 minutes or less.
- b. Up-to-date antivirus and malware installed.
- c. An up-to-date operating system with all currently available updates installed.
- d. Physical security (either card access or keyed locks) prevents unauthorized users from physically accessing the system while connected to Stronghold.
- e. All connections to Stronghold will be made through a virtual private network (VPN). Currently, Stronghold supports the OpenVPN client.

- f. Study reports, results, and published manuscripts will suppress all identifiable information and include only aggregated results.

### **3. Disruption to Service Provision**

An unanticipated problem may occur if there is an occurrence of an unanticipated event involving a disruption to harm reduction service provision as a result of the study (e.g., diversion of resources away from cities/towns randomized to the control arm that would not have otherwise occurred if the study had not been taking place).

The randomized control trial evaluates whether cities and towns receiving the PROVIDENT model predictions will have a lower overdose rate than municipalities in an intervention arm. Municipalities assigned to the control condition should receive the same overall amount of resources and mix of interventions as the treatment arm communities in accordance with the state's overdose strategic plan but without prioritization of specific neighborhoods. While the PROVIDENT model predictions are intended for cities and towns to prioritize intervention deployment to neighborhoods at high risk of future overdose *within* a city or town in the treatment arm, the model predictions are not intended to prioritize intervention deployment to neighborhoods at high risk of future overdoses over neighborhoods in the control arm. Mitigating disruption to service provisions, such as inappropriate withholding of resources from municipalities assigned to the control condition, is imperative to maintaining safety and minimizing harm throughout the trial.

We anticipate disruption to service provisions may lead to physical or psychological harm to individuals or social harm. To minimize the potential for harm, interim analyses for safety will be conducted every six months to track resource allocation within each community organization throughout the study and identify any unanticipated events constituting a disruption of typical service provision. Interim safety analyses will include assessing information collected in survey forms completed by community organizations and information gathered during focus groups. We will ask organizations to complete the forms and regularly provide information about their services in each city and town.

### **4. Changes to Trial Logistics**

An unanticipated event that changes trial logistics may constitute an unanticipated problem if it becomes clear that successful completion of the study is not feasible due to logistical or administrative reasons (e.g., changes in leadership at the Rhode Island Department of Health, significant changes to the financial resources available to fund harm reduction service provision). These changes will be monitored on an ongoing basis by the study teams at BUSPH and RIDOH and will be reported to the DSMB according to the reporting procedures described below.

### **5. Inappropriate Access by Criminal Justice**

An unanticipated problem is considered if the occurrence of an unanticipated event involves criminal justice's inappropriate access to the PROVIDENT model predictions or any information related to the trial that would not otherwise be granted. For example, if a community organization details where they are targeting their efforts as a product of using the PROVIDENT predictions during the Governor's Overdose Task Force meeting and if a police officer is in attendance, this may inadvertently lead to an increase in policing in the specified locations.

We anticipate inappropriate access by criminal justice may lead to physical or psychological harm to individuals or social harm. To minimize the risk of harm, we will conduct safety analyses every six months to monitor municipal-level data on drug-related arrests and charges. Specifically, we will compare the intervention arm and the control arm to assess changes in drug and narcotic offenses in Rhode Island at the municipal/precinct level using the National Incident-Based Reporting System. We will also conduct analyses to identify changes in the demographics of arrestees. Finally, we will ask each community organization how they are using resources and if any results have been shared with non-participating parties on a six-month basis to identify changes in access.

Any changes identified will be followed until resolved or considered stable by the Co-PIs and reported to the DSMB according to the reporting procedures described below.

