**Scope:**

This document covers (a) Phase 1 PROVIDENT model development, (b) the Phase 2 randomized cluster trial (39 Rhode Island municipalities randomized 1:1 to PROVIDENT vs comparator), (c) a parallel Phase 2 implementation study (surveys/focus groups; staff enrollment; no randomization of individuals), and (d) the COVID-19 supplement study. The ClinicalTrials.gov record (NCT05096429) reports only the Phase 2 randomized cluster trial. The implementation study, Phase 1 model development, and COVID supplement are not included.

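### The six-monthly policing check contrasts offence counts between arms, although the harm described is local; it needs a town-level screen with an alert limit

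*SAP*

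**What the plan says.** SAP section F, item 5 (Inappropriate Access by Criminal Justice) gives the example of an organisation describing its targeted areas at a meeting where a police officer is present, and warns that "this may inadvertently lead to an increase in policing in the specified locations". In response, "we will conduct safety analyses every six months to monitor municipal-level data on drug-related arrests and charges". The next sentence makes this specific: "we will compare the intervention arm and the control arm to assess changes in drug and narcotic offenses in Rhode Island at the municipal/precinct level". The data source is the National Incident-Based Reporting System (NIBRS).

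The item adds two further channels. One is demographic: "We will also conduct analyses to identify changes in the demographics of arrestees". The other is a six-monthly inquiry: "we will ask each community organization how they are using resources and if any results have been shared with non-participating parties". On follow-up it says "Any changes identified will be followed until resolved or considered stable by the Co-PIs and reported to the DSMB".

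The item states no test, error rate, baseline period, per-town flag or definition of a change. SAP section E lists "inappropriate access by criminal justice to the PROVIDENT model predictions or any information related to the trial" among the reasons for which the trial may be stopped. The Protocol's Scope gives the allocation as "39 Rhode Island municipalities randomized 1:1 to PROVIDENT vs comparator".

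**The concern.** The harm and the contrast sit at different levels. A disclosure would name particular neighbourhoods, so extra policing would show in one or a few towns. An intervention-versus-control contrast spreads such a rise over 19 or 20 towns. The data are held by municipality or precinct, but the text does not commit to judging each town against its own history.

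The check matters most for a leak that nobody reports, because the arrest data may then be the only trace. SAP F.5 expects physical, psychological or social harm from such access. If the one offence comparison written down is insensitive to a local rise, an unremarkable result says little about whether a rise occurred.

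**Working it through.** The plan states no power or detection figure for this check, so there is none to reproduce. The calculation asks how often a doubling of offences in one intervention town, in one six-month window, would be detected.

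**Inputs from the documents**
- 39 towns, 1:1, so 19 or 20 per arm (Protocol, Scope).
- Town populations and strata (SAP Table S1). The state total is 1,052,567; Providence has 178,042 (16.9%); 29 of the 39 towns have fewer than 30,000 people.
- Six-monthly looks (SAP F.5).

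**Assumed, because the documents are silent**
- Offence rate of 150, 300 or 600 per 100,000 per year.
- Between-town SD of log change, beyond Poisson variation, of 0.1, 0.2 or 0.3.
- Two-year baseline; arms judged at two-sided 5%.
- Size of rise: a doubling.

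**What the rates imply.** Expected six-month count = population × rate / 100,000 / 2.

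| | at 150 | at 600 |
|---|---|---|
| State (1,052,567) | 789 | 3,158 |
| Providence (178,042) | 134 | 534 |
| Median town, Portsmouth (17,389) | 13 | 52 |
| New Shoreham (1,051) | 0.8 | 3.2 |

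**Step 1: dilution.** With each town counted once, doubling one town shifts its arm's mean log rate by log(2)/19.5 = 0.0355. The standard error of the arm difference is SD × √(1/19 + 1/20) = 0.320 × SD, where SD is now the total town-level SD.
- SD 0.2: 0.0355/0.0641 = 0.55, and Φ(0.55 − 1.96) = 0.08, so 92% missed.
- SD 0.3: 0.0355/0.0961 = 0.37, and Φ(0.37 − 1.96) = 0.056, so 94% missed.
- SD 0.66: 96% missed.

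**Step 2: simulation with the town as the unit.** Using Table S1 populations, stratified randomisation, Poisson counts and a random intervention town doubled, inverse-variance weighted and unweighted arm contrasts together miss the doubling in about 90-96% of looks. The weighted form does better for large towns when SD is 0.1: Providence is missed 64-67% of the time and Warwick 75-79%. At SD 0.2-0.3 both exceed 90%.

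**Step 3: pooled counts.** If offences are summed within each arm and the change compared as Poisson, the average miss rate falls to 57-85% over the same grid. A separate calculation, with 500 to 4,000 offences statewide per six months and no extra variation, gives:
- median town missed 89-96%;
- 17 to 35 of the 39 towns missed at least 90% of the time;
- Providence missed 0-42%, Warwick 8-78%.

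The gain has a price. With extra town-level variation of SD 0.3, the pooled Poisson test flags upward 12-30% of the time with no leak at all.

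**Step 4: own-town screen.** Comparing each intervention town with its own baseline at a one-sided 5% limit detects the doubled town in 42-94% of looks, with roughly 0.5-0.9 false alerts per look. The chance of at least one false alert per look is 1 − exp(−0.5) = 39% to 1 − exp(−0.9) = 59%. With the 5% shared over about 20 towns, detection falls to 7-76%.

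**Step 5: repeated looks.** If the rise persisted and looks were independent, a 95% miss rate per look becomes 0.95⁴ = 81% over four looks and 0.95⁵ = 77% over five.

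**The case against.** The strongest reply is that F.5 is not confined to an arm average. It commits first to monitoring municipal-level data, gives no test or decision rule, and does not exclude looking at each town. That stands as a reading. It does not supply an own-town baseline, a limit or a definition of a change, and the only comparison of offence counts spelled out is between arms.

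A reader might infer that a null contrast would be taken as proof of no harm, or that the contrast is the only protection. The documents support neither. No sentence equates a null contrast with safety. SAP section F, Reporting Procedures for Unanticipated Problems, has the DSMB notified of any unanticipated problem and asked to convene within 30 days. Stopping reason 5 in section E attaches to the access itself, not to arrest counts. A known leak therefore reaches the DSMB whatever the offence data show. The six-monthly question on sharing, and the regular queries about unauthorised use of the Web Tool (SAP F.1), address the cause directly. They do, however, rely on self-report by organisations that may have disclosed inadvertently, and the demographic analysis has no stated unit or threshold.

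A reader might also take 90% as the miss rate under any analysis. It is not: it depends on assumed counts and SD, on a doubling as the effect, and on treating the town as the unit. Pooled counts can show a doubling in Providence.

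The comparison with the own-town screen is also not like for like: one two-sided 5% test against about 20 one-sided 5% tests. That objection stands, and the adjusted detection range of 7-76% must be stated with the proposal.

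**Conclusion.** The concern holds in a limited form. F.5 describes a local harm and specifies its only offence-count comparison as an arm contrast, with no own-town baseline or alert limit. Under the assumed rates and SDs, a town-as-unit arm test misses a one-town doubling in about 90-96% of looks. Pooled counts miss fewer, particularly in the largest towns, at the cost of false flags when variation exceeds Poisson.

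The direction follows from the dilution in Step 1. The exact percentages rest on offence counts, variation, test and effect size that the documents do not give. The consequence is a weak backstop for leaks that nobody discloses, not an absence of safeguards. It is a worthwhile, inexpensive improvement to safety monitoring and does not bear on the primary analysis.

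**What to change.** In SAP section F, item 5, add a town-level (or precinct-level) screen from the same NIBRS data:

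- For each intervention town and six-month window, report observed drug offences against the count expected from that town's own pre-trial data and the statewide trend.
- Give the ratio with its upper confidence bound.
- Preset an alert limit and send every town above it to the DSMB for review.
- Keep the arm comparison as a secondary summary, reported as a rate ratio with its interval.

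The cost is some wording, one short table per look, and false alerts. At 0.5-0.9 per look, five looks would give about 2.5 to 4.5 in total. A limit adjusted for about 20 towns reduces these but lowers detection substantially (7-76% against 42-94%), so the choice should be made openly with the DSMB. The limit also needs an estimate of each town's ordinary variation, which pre-trial data can supply. Very small towns stay weakly monitored under either limit; for them the questions on sharing remain the main protection.
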